5.3 Interim Assessment

The interim assessment will include the following tests or procedures and should occur within 14-42 days of surgery:

1. Clinical examination.
2. Documentation of key data from the pathology report: T (1-4) and N (0-3) stage, ECE status (+/-) and extent of ECE (mm), margin status (+/-).
3. Arm assignment (based on pathology data)
4. Documentation of patient symptoms using NCI-CTCAE version 4.0; please note that AEs considered at least possibly related to surgery need not be recorded.
5. Documentation of ECOG performance status.
6. Completion of QOL questionnaires.
7. Documentation of Comorbidity Index.
8. Laboratory evaluations: CBC, BMP, magnesium, PT/PTT.
9. OPTIONAL: Speech and swallowing assessment including MBS and PSS-HN questionnaire.

5.4 Postoperative Adjuvant Chemotherapy

5.4.1 ARM 1 ONLY - Cisplatin (one dose) + 21 doses of RT

The dose of cisplatin will be given on the same day as one of the initial 5 doses of POART (refer to Section 5.5 for RT dosing).

Recommended procedures for cisplatin therapy are as follows:

1. Antiemetic premedication prior to cisplatin: palonosetron 0.25 mg IVPB, dexamethasone 10 mg IVPB and aprepitant 150 mg IVPB.
2. Hydration consisting of 1L IVF NS (10 meq KCL/L + 8 meq MgSO₄/L) over 60 minutes before and after cisplatin on the day of dosing. 2L IVF NS over 60 minutes on each of the two days following cisplatin dosing.
3. Administration of cisplatin (100 mg/m² IVPB over 60 minutes) on one day only during one of the first 5 doses of radiation.
4. Physical examination will be performed on the day of cisplatin administration and on day 22 (+/- 2) and 36 (+/- 2) after starting radiation therapy.
5. Weight (kg) will be collected weekly during radiation.
6. Documentation of ECOG performance status will be done on the day of cisplatin administration and on days 22 (+/- 2) and 36 (+/- 2) after starting radiation therapy.
7. Documentation of patient symptoms using NCI-CTCAE version 4.0 will be done on the day of cisplatin administration and on days 22 (+/- 2) and 36 (+/- 2) after starting radiation therapy.
8. CBC, BMP and magnesium on the day of cisplatin administration and on days 22 (+/- 2) and 36 (+/- 2) after starting radiation therapy.
9. Patient to complete QOL questionnaire prior to starting radiation (-7/+0) and during the fourth week of radiation (radiation doses 16-21) and 36 (+/- 2) days after starting radiation therapy.
10. OPTIONAL: Patient to receive speech and swallowing assessments prior to starting radiation* and during the fourth week of radiation (radiation doses 16-21) and 2 weeks after completing radiation therapy.
*Modified barium swallow not needed within one week prior to starting radiation.

5.4.2 ARM 2: No Cisplatin. 21 doses of RT only.

Refer to Section 5.5 for RT dosing instructions.

1. Physical examination and weight (kg) will be performed on the first day of radiation therapy and on days 22 (+/- 2) and 36 (+/- 2) after starting radiation therapy.
2. Weight (kg) will be collected weekly during radiation.

3. Documentation of ECOG performance status will be done on the first day of radiation therapy and on days 22 (+/- 2) and 36 (+/- 2) after starting radiation therapy.
4. Documentation of patient symptoms using NCI-CTCAE version 4.0 will be done on the first day of radiation therapy and on days 22 (+/- 2) and 36 (+/- 2) after starting radiation therapy.
5. CBC, BMP and magnesium on the first day of radiation therapy and on days 22 (+/- 2) and 36 (+/- 2) after starting radiation therapy.
6. Patient to complete QOL questionnaire prior to starting radiation (-7/+0) and during the fourth week of radiation (radiation doses 16-21), and 36 (+/- 2) days after starting radiation therapy.
7. OPTIONAL: Patient to receive speech and swallowing assessments prior to starting radiation* and during the fourth week of radiation (radiation doses 16-21) and 36 days after starting radiation therapy.

*Modified barium swallow not needed within one week prior to starting radiation.

5.4.3 ARM 3 ONLY – Thirty doses of RT (+ 3 doses of Cisplatin if positive margins or ECE)

If the patient has positive margins or ECE, they will receive Cisplatin with the 30 doses of RT. The first dose of cisplatin will be given on one of the days during the initial 5 days of POART, the second cisplatin dose on the day of radiation dose 16 (+/- 5 days), and the third cisplatin dose on the day of radiation dose 26 (+/- 5 days).

Recommended procedures for Arm 3 are as follows:

1. Physical examination will be performed on each day of cisplatin administration (radiation dose 1, 16 (+/- 5) and 26 (+/- 5)).
2. Documentation of ECOG performance status will be done on each day of cisplatin administration (radiation dose 1, 16 (+/- 5) and 26 (+/- 5)).
3. Documentation of patient symptoms using NCI-CTCAE version 4.0 will be done on each day of cisplatin administration (radiation dose 1, 16 (+/- 5) and 26 (+/- 5)).
4. Patient to complete QOL questionnaire prior (-7/+0) to starting radiation, during the fourth week of radiation (radiation doses 16-20) and during the last week of radiation (radiation doses 26-30).
5. OPTIONAL: Patient to receive speech and swallowing assessment prior (within one week) to starting radiation*, during the fourth week of radiation (radiation doses 16-20) and during the last week of radiation (radiation doses 26-30). *Modified barium swallow not needed within one week prior to starting radiation.

Recommended procedures for cisplatin therapy (on Arm 3) are as follows:

1. Antiemetics premedication prior to each dose of cisplatin: palonosetron

0.25 mg IVPB, dexamethasone 10 mg IVPB and aprepitant 150 mg IVPB.

2. Hydration consisting of 1L IVF NS (10 meq KCL/L + 8 meq MgSO₄/L) over 60 minutes before and after cisplatin on the day of dosing. 2L IVF NS over 60 minutes on each of the two days following cisplatin dosing.
3. Administration of cisplatin (100 mg/m² IVPB over 60 minutes) on days 1, 22 (+/- 5), and 36 (+/- 5).
4. Weight (kg) will be collected weekly during radiation.
5. CBC, BMP and magnesium on each day of cisplatin administration (radiation dose 1, 16 (+/- 5) and 26 (+/- 5)).

5.5 POART

It is recommended that radiation therapy begin within 28 to 49 days (and no later than 56 days) after the surgical resection. Intensity modulated radiation therapy (IMRT) or intensity modulated proton therapy (IMPT) is to be used exclusively for this study. IMRT or IMPT will be delivered once per day Monday through Friday per routine clinical practice in Arm 3. In Arms 1 and 2, one BID treatment will be given during the course of therapy. If patient logistics prohibit the one BID treatment, once daily treatments throughout will be acceptable. The total dose to the postoperative tumor bed will be:

- Arm 1: 4200 cGy in 21 fractions of 200 cGy each over 4 weeks
- Arm 2: 4200 cGy in 21 fractions of 200 cGy each over 4 weeks
- Arm 3: 6000 cGy in 30 fractions of 200 cGy each over 6 weeks

Additional regions in the ipsilateral and contralateral neck at risk for microscopic disease in the cervical lymph nodes will receive:

- Arm 1: 3780 cGy in 21 fractions of 180 cGy each
- Arm 2: 3780 cGy in 21 fractions of 180 cGy each
- Arm 3: 5200 cGy in 30 fractions of 173 cGy each

5.5.1 CT Simulation

As per routine practice, computed tomography (CT) will be the primary image platform for targeting and treatment planning. Prior to the scan, the patient will be given IV contrast according to institutional protocols (provided the patient has normal renal function and no allergies to contrast). The patient will be positioned supine on the CT simulator table (head toward the gantry). The head will be placed on standard or customized headrest so as to have the neck slightly extended. Alternatively, a custom head/shoulder mold may be used for immobilization. An immobilization mask will then be fashioned. A CT dataset will be acquired from the top of the head through 5 cm below the clavicular heads with no more than 5 mm axial slices. Three localization marks will be drawn and wired on the patient's immobilization mask at the angle of the mandible bilaterally and midline. These marks will serve to establish an internal reference from which an isocenter is placed

midline, midplane, at the level of the angle of the mandible.

5.5.2 Virtual Simulation and Contouring

The CT scan will be exported to a commercially available virtual simulation software package. Guidelines for delineating each lymph node level will be based on the international consensus for delineation of head and neck lymph nodes (<http://www.rtoq.org/hnatlas/main.html>). These guidelines were derived in part from Washington University School of Medicine institutional data and are consistent with routine clinical practice at Washington University.

Arms 1 and 2: An example case of a T3N2BM0 (AJCC 7th edition), stage IVA tonsil cancer is outlined in the table below. Current treatment guidelines for this case including dose levels are represented with CTV1 and CTV2.

CTV1	CTV2
[GTVp + GTVn] + 1.0 to 1.5 cm minimum concentric margin excluding bone and air with aid of preop imaging with/without fusion	IN (II-V) + BRPLN + CN (IIb-IV) Exclusive of CTV1.
Dose 42 Gy/21 fx	Dose 37.8 Gy/21 fx

Key: GTVp = GTV primary tumor; GTVn = GTV nodal tumor; IN = ipsilateral neck; CN = contralateral neck; roman numbers relate to the level system of naming lymph node regions; BRPLN = bilateral retropharyngeal lymph nodes).

Arm 3: An example case of a T4N2M0 (AJCC 7th edition), stage IVA tonsil cancer is outlined in the table below. Current treatment guidelines for this case including dose levels are represented with CTV1 and CTV2.

CTV1	CTV2
[GTVp + GTVn] + 1.0 to 1.5 cm minimum concentric margin excluding bone and air with aid of preop imaging with/without fusion	IN (II-V) + BRPLN + CN (IIb-IV) Exclusive of CTV1.
Dose 60 Gy/30 fx	Dose 52 Gy/30 fx

Key: GTVp = GTV primary tumor; GTVn = GTV nodal tumor; IN = ipsilateral neck; CN = contralateral neck; roman numbers relate to the level system of naming lymph node regions; BRPLN = bilateral retropharyngeal lymph nodes).

Normal structure and treatment volume contours will be delineated in a manner consistent with routine clinical practice.

5.5.3 IMRT and/or IMPT Optimization

The image and contour data will be exported to the Varian Eclipse platform where IMRT or IMPT optimization will be performed.

5.5.4 Treatment Field Arrangement

The Varian System employs up to ten co-planar fields with static or dynamic multileaf collimation. The treatment planning system calculates the optimized collimator leaf delivery pattern that most closely approximates the prescribed constraints and prescription goals.

5.5.5 Dose, Energy and Prescription Parameters

Arms 1 and 2: External beam radiation with 6 MV photons will be delivered in 200 cGy daily fractions (Monday through Friday), 21 fractions over 4 weeks to a total dose of 4200 cGy.

Prescription Coverage Goals

99% of clinical treatment volumes should receive at least 95% of the respective prescription dose (i.e. 99% of PTV 4200 should be covered by 3990 cGy and 99% of PTV 3780 covered by 3591 cGy).

No more than 5% of the volume “Skin” should receive more than the prescription dose (42 Gy) and hotspots must be within the PTV.

Arm 3: External beam radiation with 6 MV photons will be delivered in 200 cGy daily fractions (Monday through Friday), 30 fractions over 6 weeks to a total dose of 6000 cGy.

Prescription Coverage Goals

99% of clinical treatment volumes should receive at least 93% of the respective prescription dose (i.e. 99% of PTV 6000 should be covered by 5700 cGy, and 99% of PTV 5200 covered by 4940 cGy).

No more than 5% of the volume “Skin” should receive more than the prescription dose (60 Gy) and hotspots must be within the PTV.

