5.5.7 Treatment Plan Evaluation

The plan will be reviewed by the treating physician prior to treatment in order to ensure that all parameters have been met. Isodose curves and dose volume histograms (DVH) will be analyzed.

Arms 1 and 2: Criteria for plan evaluation will include:

- Isodose Curves:

The 95% isodose line must be generally conformal to the PTV with visually acceptable tumor coverage and visually acceptable critical structure avoidance.

The 110% isodose line must not include any critical structure volumes.

The 4200 cGy isodose line must not encroach on the “Spinal cord + 5 mm”.

The 2600 cGy isodose line should spare parotid glands when possible.
- Dose Volume Histograms (DVHs):

No more than 20% of any PTV should exceed 110% of the prescribed dose.

DVH from PTVs must meet all prescription parameters.

Normal structure DVHs should meet constraint parameters as listed above.

Arm 3: Criteria for plan evaluation will include:

- Isodose Curves:

The 95% isodose line must be generally conformal to the PTV with visually acceptable tumor coverage and visually acceptable critical structure avoidance.

The 110% isodose line must not include any critical structure volumes.

The 4200 cGy isodose line must not encroach on the “Spinal cord + 5 mm”.

The 2600 cGy isodose line should spare parotid glands when possible.

- Dose Volume Histograms (DVHs):
No more than 20% of any PTV should exceed 110% of the prescribed dose.
DVH from PTVs must meet all prescription parameters.
Normal structure DVHs should meet constraint parameters as listed above.

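### The Arm 3 target-coverage goal is printed as 93% of prescription, but the doses that define it are exactly 95%

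*Combined protocol and SAP*

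**What the plan says.** Section 5.5.5 gives prescription coverage goals separately for Arms 1 and 2 and for Arm 3.

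- **Arm 3:** the goal is that "99% of clinical treatment volumes should receive at least 93% of the respective prescription dose". Within the same sentence this is restated in absolute dose as "99% of PTV 6000 should be covered by 5700 cGy, and 99% of PTV 5200 covered by 4940 cGy".
- **Arms 1 and 2:** the goal is that "99% of clinical treatment volumes should receive at least 95% of the respective prescription dose", restated as "99% of PTV 4200 should be covered by 3990 cGy and 99% of PTV 3780 covered by 3591 cGy".

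The Arm 3 tumour-bed prescription in section 5.5 is "Arm 3: 6000 cGy in 30 fractions of 200 cGy each over 6 weeks". The same section gives 5200 cGy in 30 fractions to the neck regions at risk, and the contouring table in section 5.5.2 repeats 60 Gy and 52 Gy.

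Section 5.5.7 makes these goals part of plan acceptance. It states that "The plan will be reviewed by the treating physician prior to treatment in order to ensure that all parameters have been met" and, for each group of arms, that "DVH from PTVs must meet all prescription parameters". Its isodose criterion, worded identically for all arms, is that "The 95% isodose line must be generally conformal to the PTV".

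**The concern.** The Arm 3 sentence introduces its two doses as the meaning of its percentage, so percentage and doses should be one requirement written two ways. They are not. The percentage is looser than the doses in both target volumes.

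This is a working threshold that is checked before treatment. A plan that delivers 5600 cGy to 99% of PTV 6000 reaches 5600/6000 = 93.3% of prescription. It meets the printed percentage and misses the printed dose, so the section both passes and fails it. A planner who carried only the percentage into the planning system would set the goal too low. The arm concerned is the one for clinical or pathologic T4 or clinical N3 disease, which section 1.9 describes as high risk and assigns to standard intensive therapy. Nothing in the protocol explains why it should have a lower coverage goal than the de-intensified arms.

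**Working it through.** **Inputs**

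| Item | Arm 3 | Arms 1 and 2 | Source |
|---|---|---|---|
| Prescription, tumour bed | 6000 cGy | 4200 cGy | 5.5, 5.5.2 |
| Prescription, neck at risk | 5200 cGy | 3780 cGy | 5.5, 5.5.2 |
| Coverage percentage | 93% | 95% | 5.5.5 |
| Coverage dose, tumour bed | 5700 cGy | 3990 cGy | 5.5.5 |
| Coverage dose, neck at risk | 4940 cGy | 3591 cGy | 5.5.5 |

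**Step 1. Try to reproduce the plan's own figures (percentage × prescription).**

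- Arms 1 and 2, as a control: 0.95 × 4200 = 3990 and 0.95 × 3780 = 3591. Both printed doses are reproduced.
- Arm 3: 0.93 × 6000 = 5580, against 5700 printed. 0.93 × 5200 = 4836, against 4940 printed. Neither is reproduced.

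**Step 2. Find the percentage that the Arm 3 doses imply (coverage dose / prescription).**

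- 5700/6000 = 0.95
- 4940/5200 = 0.95

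Both are exact, so rounding plays no part.

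**Step 3. Size of the gap.**

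- PTV 6000: 5700 − 5580 = 120 cGy, and 120/6000 = 2%.
- PTV 5200: 4940 − 4836 = 104 cGy, and 104/5200 = 2%.

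**Step 4. Could the prescriptions be wrong instead?** For the printed doses to be 93%, the prescriptions would have to be 5700/0.93 ≈ 6129 cGy and 4940/0.93 ≈ 5312 cGy. Neither value appears anywhere in the protocol, while 60 Gy and 52 Gy are stated consistently.

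**Step 5. Which figure is in error?** If 93% were intended, both Arm 3 doses would have to be wrong and would have to land on exactly the same other ratio, the one used for the remaining arms. A single wrong digit in the percentage explains everything.

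**The case against.** The strongest counter-argument is that the sentence corrects itself. Both doses stand next to the percentage, they are the stricter limit, and section 5.5.7 asks that all parameters be met. Someone would have to ignore half the sentence to be misled, and each plan also has a dose-volume review and physics quality assurance (sections 5.5.7 and 5.5.9). This is fair, and it limits the practical risk. It does not make the sentence consistent.

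Four further points deserve weight.

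- **Possible misread character.** The electronic text shows slips of this kind elsewhere, such as the letter O for zero in the nodal staging tables of section 1.6. A 5 misread as a 3 cannot be excluded. The other figures in section 5.5.5 are mutually consistent, so there is no positive sign of it, but the protocol page should be looked at before an amendment is raised.
- **Soft wording.** These are called goals, they are phrased with should, and section 5.5.6 ranks them below critical structures. That is true, but section 5.5.7 then says that the target-volume histograms must meet them.
- **The isodose criterion is weak support.** It asks for general conformity and visually acceptable coverage, and it is not a numeric volume threshold. If the line is normalised to 6000 cGy, which the protocol does not state, it lies at 0.95 × 6000 = 5700 cGy. That is above the whole PTV 5200 prescription and says nothing about coverage of that volume. The case for 95% therefore rests on the two Arm 3 doses and the parallel goal, with the isodose line as a minor addition.
- **Small arm, no hypothesis.** Section 10.2 estimates 6 patients in Arm 3, and section 1.9 sets no formal recurrence hypothesis for it. This limits the consequence. It is no reason to leave an acceptance threshold ambiguous.

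**Conclusion.** The concern holds. The percentage and the doses in the Arm 3 coverage goal cannot both be right, and the evidence points to 95% as the intended value. The protocol does not state the intent, so this is a strong inference and not a documented fact. It also assumes that the protocol page really shows 93%.

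The discrepancy is 2% of prescription in each volume, and it matters only to someone who works from the percentage alone. The 60 Gy and 52 Gy prescriptions stand. No effect is claimed on recurrence results, the weight-loss endpoint or power. It should be corrected because it is a dose parameter checked before each patient is treated, not because it threatens the trial's conclusions.

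**What to change.** In the Arm 3 paragraph of section 5.5.5, change 93% to 95% and leave 5700 cGy and 4940 cGy as they are. Check the figure against the protocol page first, and have the radiation team confirm the intended value. The goal then agrees with its own doses and with the goal for Arms 1 and 2. If the team did intend 93%, the doses would have to become 5580 and 4836 cGy, with a reason given for the looser goal in this arm.

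The cost is a one-figure correction, with no change to prescription, sample size or analysis.

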5.5.6 Normal Structure Dose Limit Guidelines

Arms 1 and 2: Dose limit guidelines for normal structures are as follows:

Structure	Volume	Dose Guideline (Gy)	Dose Mean (Gy)
Critical Structures			
Spinal Cord + 8 mm	1 cc	42	
Spinal Cord	0.1 cc	40	

Brainstem	1%	40	
	0.1 cc	40	
Brain	1%	40	
	5 cc	45	
Optic nerve*	1%	40	
	0.1 cc	42	
Optic chiasm	1%	40	
	0.1 cc	42	
Eye*			45
Normal Structures			
Retina*	1%	40	25
Lens*			2
Oral cavity			35
Larynx			42
Mandible	5%	45	
Skin	5%	45	
Partial esoph	2 cc	40	
Middle Ear*			45
Parotid glands*	20 cc	20	26

*Paired structures. Dose constraints apply to one such structure and are equivalent for the contralateral side.

Priority for Above Dose Constraints

1. Critical Structures
2. PTV Prescription Goals
3. Salivary Glands
4. Other Structures

Arm 3: Dose limit guidelines for normal structures are as follows:

Structure	Volume	Dose Guideline (Gy)	Dose Mean (Gy)
Critical Structures			
Spinal Cord + 8 mm	1 cc	50	
Spinal Cord	0.1 cc	45	
Brainstem	1%	60	
	0.1 cc	60	
Brain	1%	60	
	5 cc	65	
Optic nerve*	1%	60	
	0.1 cc	60	
Optic chiasm	1%	60	
	0.1 cc	60	
Eye*			45
Normal Structures			
Retina*	1%	50	35
Lens*			2
Oral cavity			35

Larynx			45
Mandible	5%	73.5	
Skin	5%	70	
Partial esoph	2 cc	54	
Middle Ear*			45
Parotid glands*	20 cc	20	26

*Paired structures. Dose constraints apply to one such structure and are equivalent for the contralateral side.

Priority for Above Dose Constraints

1. Critical Structures
2. PTV Prescription Goals
3. Salivary Glands
4. Other Structures

5.5.7 Treatment Plan Evaluation

The plan will be reviewed by the treating physician prior to treatment in order to ensure that all parameters have been met. Isodose curves and dose volume histograms (DVH) will be analyzed.

Arms 1 and 2: Criteria for plan evaluation will include:

- Isodose Curves:

The 95% isodose line must be generally conformal to the PTV with visually acceptable tumor coverage and visually acceptable critical structure avoidance.

The 110% isodose line must not include any critical structure volumes.

The 4200 cGy isodose line must not encroach on the “Spinal cord + 5 mm”.

The 2600 cGy isodose line should spare parotid glands when possible.
- Dose Volume Histograms (DVHs):

No more than 20% of any PTV should exceed 110% of the prescribed dose.

DVH from PTVs must meet all prescription parameters.

Normal structure DVHs should meet constraint parameters as listed above.

Arm 3: Criteria for plan evaluation will include:

- Isodose Curves:

The 95% isodose line must be generally conformal to the PTV with visually acceptable tumor coverage and visually acceptable critical structure avoidance.

The 110% isodose line must not include any critical structure volumes.

The 4200 cGy isodose line must not encroach on the “Spinal cord + 5 mm”.

The 2600 cGy isodose line should spare parotid glands when possible.

- Dose Volume Histograms (DVHs):
No more than 20% of any PTV should exceed 110% of the prescribed dose.
DVH from PTVs must meet all prescription parameters.
Normal structure DVHs should meet constraint parameters as listed above.

5.5.8 Daily Radiation Treatment

Arms 1 and 2: Patients will receive external beam radiation treatment delivered by a Varian linear accelerator once a day, five days a week, for 4 to 4 1/5 weeks as per routine clinical practice.

Arm 3: Patients will receive external beam radiation treatment delivered by a Varian linear accelerator once a day, five days a week, for 6 weeks as per routine clinical practice.

5.5.9 Quality Assurance

Treatment plan physics review and QA are required for each patient in accordance with current institutional standards for IMRT.

Daily set-up error will be minimized by the following clinically approved and commercially available patient setup techniques: immobilization mask, standard skin/mask alignment marks, and daily on-board imaging.

Per routine practice, daily cone beam CT scans will be acquired and compared with planning CT overlay.

These setup scans will be performed immediately prior to each treatment and the appropriate shifts will be made at that time.

